### 7.2.3 Vital Signs, Physical Findings and Other Safety Assessments

Safety assessments will include physical examination, vital signs, biochemistry, haematology and urinalysis laboratory screens (see Schedule of Study Assessments, Appendix 1 for Module 1, Appendix 2 for Module 2 and Appendix 9 for Module 3). Measurements of heart rate, body temperature, blood pressure and respiratory rate will be made after the patient has been resting supine for a minimum of 5 minutes. Adverse events will also be noted at every clinical visit and recorded at least every week. For all administrations in hospital, the patients must wait for at least 60 minutes from the time of the RXC004 administration for observation and repeat vital signs. Performance status will be measured weekly in cycle 1, thereafter at the beginning of each cycle.

## 7.3 Pharmacokinetics and Pharmacodynamics

### 7.3.1 Pharmacokinetic Endpoints

RXC004 PK data will be summarised using descriptive statistics (N, mean, SD, median, min, max for all parameters, also geometric mean for  $C_{max}$  and AUC) to determine the pharmacokinetic behaviour of RXC004 on multiple dosing and to confirm relevant exposure to RXC004. This may also permit investigation of any significant metabolites. Venous blood samples (2 mL) for determination of concentrations of RXC004 in plasma will be taken at the times presented in Table 10. The date and time of collection of each sample will be recorded. Samples will be split, one for RXC004 and one for the metabolite identification work.

The timing of the PK samples may be adjusted during the study, dependent on emerging data, in order to ensure appropriate characterisation of the plasma concentration-time profiles. After 2 or more cohorts have been completed the timing of later PK samples will be re-assessed based on emerging PK data and the desire to characterise 80% of the AUC in all patients. The total number of samples and the total volume of blood taken from each patient will not exceed that presented in Table 10.

If a patient misses any doses of RXC004 within 3 days of PK sampling, please contact the IQVIA representative as to any effect on the changes required on the timing of the PK assessments. All other assessments, including laboratory safety assessments, vital signs and RECIST should continue to be performed as per study plan, relative to baseline assessments.

Samples will be collected, labelled, stored and shipped as detailed in the Laboratory Manual.

Any residual sample remaining after PK analysis has been performed may be used for exploratory biomarker research and characterisation of metabolites, if consent for this exploratory research has been obtained.

### 7.3.2 Determination of Drug Concentration in Pharmacokinetic Samples

Samples for determination of RXC004 concentrations in plasma will be analysed using an appropriate bioanalytical method. Full details of the analytical method used will be described in a separate bioanalytical report.

All samples still within the known stability of the analytes of interest at the time of receipt by the bioanalytical laboratory will be analysed.

In addition, the pharmacokinetic samples may be subjected to further analyses in order to investigate the presence and/or identity of drug metabolites. Any results from such analyses will be reported separately from the Clinical Study Report.

PK parameters will be estimated for each patient using WinNonlin® (Phoenix 64 Build 8.0.0.3176) or suitable alternative. The following parameters will be derived, where appropriate, from the individual plasma concentration versus time profiles of RXC004.

**Table 9: Definition of PK Parameters**

PARAMETER	DEFINITION
$C_{max}$	The maximum observed concentration.
$t_{max}$	The time at which $C_{max}$ was apparent.
$AUC_{0-t}$	The area under the concentration versus time curve from time zero to the sampling time at the last quantifiable concentration ( $C_t$ ) at $t_{last}$ (the time of the last quantifiable concentration) calculated by the linear trapezoidal rule.
$\lambda_z$	The apparent terminal rate constant, estimated using the negative slope of the least square regression analysis of the log concentration versus time data for the terminal linear portion of the curve.
$t_{1/2}$	The apparent terminal half-life, calculated from $\text{Log}_e 2 / \lambda_z$ .
$AUC_{0-\infty}$	The area under the concentration-time curve estimated from time zero to infinity as the sum of the two areas: $AUC_{0-t}$ and $AUC_{extrap}$ , where $AUC_{extrap}$ is calculated as $C_t / \lambda_z$ .
CL	The systemic clearance calculated as: $\text{Dose} / AUC_{0-\infty}$ .
$V_{ss}$	The apparent volume of distribution at steady state calculated as: $\text{Dose} / AUC \times (AUMC / AUC_{0-\infty} - T/2)$ where T is the duration of intravenous injection.

Where appropriate the following pharmacokinetic parameters will be estimated

**Single dose:**

**Plasma**

- Maximum plasma concentration ( $C_{\max}$ )
- Time to  $C_{\max}$  ( $t_{\max}$ )
- Concentration at 24 hours ( $C_{24}$ ) (and concentration at 12 hours ( $C_{12}$ ) if start with twice daily dosing)
- Terminal rate constant ( $\lambda_z$ )
- Terminal half-life ( $T_{1/2}$ )
- Area under the plasma concentration-time curve from zero to 24 hours ( $AUC_{0-24}$ ), from zero to the time of the last measurable concentration ( $AUC_{0-t}$ ) and from zero to infinity (AUC)
- Plasma clearance (CL/F)
- Apparent volume of distribution ( $V_z/F$ )
- Mean residence time (MRT)

**Multiple dose:**

**Plasma:**

- Maximum plasma concentration at steady-state ( $C_{ss,\max}$ )
- Time to  $C_{ss,\max}$  ( $t_{ss,\max}$ )
- Minimum concentration at steady-state ( $C_{ss,\min}$ )
- Area under the plasma concentration-time curve in the dosing interval (AUCtau)
- Plasma clearance at steady-state (CLss/F)
- Mean residence time at steady-state (MRTss)
- Swing

**PK Analysis for Day 1 and Cycle 2 Day 1 (pre-dose):**

- Dose proportionality
- 
- Accumulation Ratio (Rac)
- Dose normalised Cmax
- Dose normalised AUCs
-

Plasma and pharmacodynamic samples will be collected according to the schedule in Table 10. These samples will be collected from the following patients:

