# For Module 3 the ‘on treatment’ PK full time course will take place on C1D11 (see Schedule of Assessments - Appendix 9, for more details)

### 7.3.3 Pharmacodynamic Endpoints

#### 7.3.3.1 Module 1

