8. Consenting patients will have a 10 mL blood sample taken for preparation of a germ-line DNA sample at Screening (recommended time-point only).

9. Patients will have PK blood sampling conducted at the following sample times

Cycle 0: Day 1 - Predose, then 30 mins, 1 h, 2 h, 4 h, 6 h, 8 h, 10 h, 12 h, 24 h, 48 h, 72 h and 96h post-dose.

Cycle 1, Day 15: Predose, then 30 mins, 1 h, 2 h, 4 h, 6 h, 8 h, 10 h, 12 h & 24 h

Cycle X, Day 1 - A single pre-dose sample will also be taken on Cycles 1-6 on Day 1.

Each schedule will not exceed 12 samples taken out to 96 hours post RXC004 administration. The SRC may advise on adjusted time-points. The actual time for each blood draw must be accurately recorded.

10. The Final Study Visit should be performed as soon as practically possible after discontinuation of study drug (ideally within 7 days)

11. Vitamin D (800 IU OD) and calcium (1000 to 1500 mg OD) supplementation should commence at screening and continue throughout the treatment period

12. Fresh blood may be requested from investigator sites in close proximity to RedX laboratories. All samples should be taken predose

13. Blood samples will be taken to obtain ctDNA, pre-dose at C0D1 visit, approx. 4-6hrs post dose at C2D1 and C4D1 visits, and at disease progression/discontinuation of study treatment

14. Day 1 and Day 15 bone markers will be assessed on Cycle 2 and Cycle 3 for the first 3 cohorts only (0.5mg, 1mg and 1.5mg RXC004). All subsequent cohorts will have bone markers assessed on Day 1 only of Cycle 2 and Cycle 3

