**Footnotes - General**

Assessments made on Day 1 of each cycle are to be conducted prior to RXC004 administration, unless specified otherwise.

Additional assessments may be conducted as clinically indicated.

A tolerance of +/-1 day will be permitted for all study visits and a tolerance of -1 day for all assessments relative to the study visit, unless specified otherwise.

\* Female patients, if fertile, will require a serum pregnancy test at Screening and urine pregnancy on Day 1 of each cycle

\*\*Eligibility criteria to be re-checked at Cycle 1 prior to dose administration.

\*\*\*A lateral T & L spine assessment if a Vertebral Fracture Assessment (VFA) cannot be completed locally

- a A full physical examination is required at Screening and prior to Day 1 of each cycle ; Symptom-directed physical examination is acceptable at other time-points
- b Vital signs (heart rate, BP, temperature and respiration rate) will be assessed pre-dose and up to 1 hour after the RXC004 administration. Patient status will be monitored during RXC004 administration and repeat vital signs will be taken if needed. Height is required at screening only. Weight will be recorded at Screening and on Day 1 of each cycle.
- c Pre-first dose on Cycle 0 Day 1 and 4-6hrs post dose on Cycle 1 Day 15 and Day 1 of each subsequent cycle
- d Fresh blood samples to be collected from selected sites only (in close proximity to RedX laboratory). All samples should be collected pre-dosing.
- e Pre-first dose on Cycle 0 Day 1 and 4-6hrs post dose on Day 1 of each subsequent cycle and at progression/discontinuation
- f Patients will have PK blood sampling conducted at the following sample times  
 Cycle 0: Day 1 - Predose, then 30 mins, 1 h, 2 h, 4 h, 6 h, 8 h, 10 h, 12 h, 24 h, and 48 h post-dose.  
 Cycle 1, Day 15: Predose, then 30 mins, 1 h, 2 h, 4 h, 6 h, 8 h, 10 h, 12 h & 24 h  
 Cycle X, Day 1 - A single pre-dose sample will also be taken on subsequent samples on Day 1.  
 The SRC may advise on adjusted time-points. The actual time for each blood draw must be accurately recorded.
- g An optional 'on treatment' biopsy at C1D15 and during Cycle 3 of treatment, preferably from the same site as the baseline biopsy sample
- h On Cycle 0, Day 1 and Cycle 1, Day 1 a resting 12-lead ECG will be conducted pre-dose and 30 mins (+/- 15 mins) after RXC004 administration. On Day 1 of all other cycles, a resting 12-lead ECG will be conducted pre-dose only.

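### Protocol section 7.3.2 ties the accumulation ratio and dose-normalised Cmax and AUC to Cycle 2 Day 1, which has one pre-dose sample and in Module 3 follows the off-drug days

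*Protocol*

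**What the plan says.** Protocol section 7.3.2 has three lists of PK parameters. The single-dose list and the multiple-dose list name no visit. The third list does; it is headed "PK Analysis for Day 1 and Cycle 2 Day 1 (pre-dose" and contains dose proportionality, "Accumulation Ratio (Rac", dose-normalised Cmax and "Dose normalised AUCs". It makes no distinction between modules and does not define Rac.

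The sampling schedule for these visits is:

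- **C2D1.** Table 10 marks only the pre-dose column. Appendix 1, footnote 9 agrees for Module 1: "A single pre-dose sample will also be taken on Cycles 1-6 on Day 1". Footnote f of Appendix 2 (Module 2) and of Appendix 9 (Module 3) say the same: "A single pre-dose sample will also be taken on subsequent samples on Day 1".
- **On-treatment profile.** In Module 1 it is "Cycle 1, Day 15: Predose, then 30 mins, 1 h, 2 h, 4 h", continuing to 24 h, and Module 2 uses the same visit. For Module 3 the Table 10 footnote says the "PK full time course will take place on C1D11".
- **Cycle 0 Day 1 (C0D1).** A full profile is taken in every module.

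Table 9 defines Cmax as "The maximum observed concentration" and AUC as a trapezoidal area over the sampled times. The SAP (sections III and X) leaves parameter derivation to a separate PK plan, which is not among the documents, and names no visit for these parameters.

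**The concern.** Cmax and AUC both need samples after a dose. The visit named as the multiple-dose half of the comparison has none, so the multiple-dose part of the list cannot be produced from it.

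Module 3 has a second problem. Its C2D1 visit comes at the end of the off-drug interval. Someone who applied the stated visit by forming a trough ratio would get a number describing elimination over several days and would report it as accumulation. The SAP sets concentrations below quantification to 0 in descriptive statistics (section X), so the numerator could be exactly zero. The assay limit is not given, so how often that would happen cannot be judged.

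PK after single and multiple dosing is a secondary objective in all modules, and PK is the first item Module 3 sets out to investigate.

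**Working it through.** The plan states no figure to reproduce, so the check has two parts.

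**1. Samples per visit (Table 10 and the schedule footnotes)**

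| Visit | Samples | Cmax / AUC derivable? |
|---|---|---|
| C0D1 | 13 (Module 1, with 72 h and 96 h), 11 (Modules 2 and 3) | Yes |
| C1D15 (Modules 1-2), C1D11 (Module 3) | 10, pre-dose to 24 h | Yes |
| C2D1 | 1, pre-dose | No |

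**2. What a trough ratio at C2D1 would measure**

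Inputs from the protocol:

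- Human half-life T of 11 to 13 h (section 5.4.5).
- Module 3 schedules (section 5.4.4). Arm 1 doses on days 1-4, 8-11 and 15-18; Arm 2 on days 1-14. C2D1 is day 22.
- Daily dosing in Modules 1 and 2, so C2D1 pre-dose is about 24 h after the last dose.

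Time from last dose to C2D1 in Module 3:

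- Arm 1: (22 − 18) × 24 = 96 h, or 7.4 to 8.7 half-lives.
- Arm 2: (22 − 14) × 24 = 192 h, or 14.8 to 17.5 half-lives.

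Assumption (not in the documents): one-compartment first-order decay with superposition of doses. Let r = 2^(−24/T) be the fraction remaining after 24 h. Relative to the single-dose C24:

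- Continuous daily dosing: 1/(1 − r)
- Arm 1 at C2D1: r³ (1 + r + r² + r³)(1 + r⁷ + r¹⁴)
- Arm 2 at C2D1: r⁷ (1 − r¹⁴)/(1 − r)

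At T = 12 h, r = 0.25:

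- Continuous: 1/0.75 = 1.33
- Arm 1: 0.015625 × 1.328 × 1.00006 = 0.021
- Arm 2: 0.000061 × 1.333 = 0.00008

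| T (h) | Daily dosing, C2D1/C24 | Arm 1, C2D1/C24 | Arm 2, C2D1/C24 | Arms 1 and 2, ratio on C1D11 |
|---|---|---|---|---|
| 11 | 1.28 | 0.014 | 0.00003 | 1.28 |
| 12 | 1.33 | 0.021 | 0.00008 | 1.33 |
| 13 | 1.39 | 0.030 | 0.00018 | 1.38-1.39 |
| 15 (sensitivity, assumed) | 1.49 | 0.053 | 0.0006 | 1.48-1.49 |

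Day 11 is a dosing day in both arms. In Arm 1 it is the fourth consecutive dose, so accumulation has reached at least 1 − r⁴ of the daily-dosing plateau: 99.4% at T = 13 h (r = 0.278, r⁴ = 0.006).

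**Cross-check against the protocol's own simulation.** Section 5.4.5 gives 14% and 24% of a 21-day cycle (504 h) below the IC50. Taking that time to fall at the end of the off-drug intervals:

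- Arm 1: 0.14 × 504 / 3 = 23.5 h at the end of each 96 h interval.
- Arm 2: 0.24 × 504 = 121 h of the 192 h interval.

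The C2D1 pre-dose sample is then below the IC50 in both arms. Appendix 9 also treats that time point as off drug in its skin-biopsy footnote.

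**The case against.** The heading names Day 1 as well as C2D1. C0D1 has a full profile, so dose proportionality and dose-normalised Cmax and AUC can be derived for the single dose. The words marking C2D1 as pre-dose suggest the authors knew it gives only a trough. With daily dosing, that trough over the C24 from C0D1 is a usable accumulation ratio. This stands: in Modules 1 and 2 a trough-based Rac works, with an expected value of about 1.28-1.39.

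A reader might infer that the steady-state PK objective is lost. The documents do not support that. The multiple-dose list in section 7.3.2 covers steady-state Cmax, Cmin, AUC over the dosing interval, clearance and more, and the C1D15/C1D11 profile supplies the data for it. A reader might also infer that Rac will in fact be computed from C2D1. That cannot be shown, since the separate PK plan may already name the right visit.

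The list looks written for the escalation modules: dose proportionality has little role in Module 3, where every patient starts at 2 mg. That explains the mismatch but does not remove it, because the heading applies to all modules. The blank bullets in the list may be text lost in conversion, and nothing here rests on them.

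**Conclusion.** Wrong as written, and minor. The defect has two parts:

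- In every module, no multiple-dose Cmax or AUC, and no Rac built on them, can come from C2D1.
- In Module 3, a C2D1 trough ratio would measure washout: about 0.014-0.030 in Arm 1 and 0.00003-0.0002 in Arm 2, against about 1.3-1.4 on a dosing day. Arm 2 is the only schedule in the SAP's Module 3 intermittent dose table, so the more extreme case is the relevant one.

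The sample counts rest on the documents alone. The ratios rest on the one-compartment assumption, on reading Rac as C2D1 over C24 (the protocol gives no definition), and on nominal visit days. A 15 h half-life does not change the conclusion. Appendix 9 allows C2D1 to move by 3 days. With the dosing days unchanged, a visit 3 days early would shorten the interval to 24 h in Arm 1 and 120 h in Arm 2, so in Arm 1 the ratio would also depend on when the visit took place.

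PK is summarised descriptively with no hypothesis test, and all the samples needed are already scheduled. The consequence is therefore limited to these derived parameters.

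**What to change.** In protocol section 7.3.2, and in the separate PK plan if it repeats the heading:

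- Name C0D1 and the Cycle 1 on-treatment profile (C1D15 for Modules 1 and 2, C1D11 for Module 3) as the visits for dose proportionality, Rac and the dose-normalised parameters.
- Define Rac as AUC over 24 h in that Cycle 1 profile divided by AUC0-24 on C0D1.
- Report C2D1 only as a trough in Modules 1 and 2 and as an off-drug concentration in Module 3.
- The SAP (section I) indicates that the Module 1 database is already locked, so state in that module's report which visit was used for Rac.

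The cost is a wording change. No visit, sample or assay is added.

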**Table 10: PK Plasma Sampling Schedule**

Study Visit	Timing of Sample Relative to RXC004 Administration												
	Pre-dose	0.5 h (± 10 min)	1 h (± 10 min)	2 h (± 30 min)	4 h (± 30 min)	6 h (± 30 min)	8 h (± 30 min)	10 h (± 30 min)	12 h (± 30 min)	24 h (± 1h)	48 h (± 2h)	72 h* (± 2h)	96 hr* (± 2h)
C0D1	X	X	X	X	X	X	X	X	X	X	X	X	X
C1D1	X												
C1D15#	X	X	X	X	X	X	X	X	X	X			
C2D1	X												
C3D1to C6D1	X												

\*72hr and 96hr PK will be completed in the first cohort of module 1 (RXC004 monotherapy), but may be stopped for subsequent cohorts if the terminal elimination phase indicates that this is not required. 72hr and 96hr PK is not required for Module 2 (RXC004 and nivolumab combination) and Module 3 (intermittent RXC004 schedules)

# For Module 3 the ‘on treatment’ PK full time course will take place on C1D11 (see Schedule of Assessments - Appendix 9, for more details)

### 7.3.3 Pharmacodynamic Endpoints

#### 7.3.3.1 Module 1

##### Skin, blood and tumour Sample Collection

Skin punch biopsy samples will be collected, where possible and where consent has been given, from any suitable patient enrolled into Module 1, according to the schedule of assessments. These samples will be collected at baseline and on treatment.

PBMC, plasma and ctDNA samples for pharmacodynamic analysis will be collected from all patients at baseline and on treatment, according to the schedule of assessments.

Fresh whole blood will be collected from a subset of patients at baseline and on treatment, according to the table of scheduled assessments (depending on proximity of site for analysis of this fresh sample).

Optional paired tumour biopsies will be also collected, where possible, from any suitable patient enrolled into module 1.

As pharmacodynamic data become available, the timing of pharmacodynamic sampling may be adjusted, but the frequency of blood samples obtained will not increase.

**Table 11: Module 1 : Pharmacodynamic samples / Tumour Collection Schedule**

Study Visit	Tissue samples		Blood samples			
	Skin punch biopsy	Tumour Collection (optional)	PBMC	Plasma	ctDNA	Fresh whole blood a
C0D1	Pre-dose b	Pre-dose b	Pre-dose	Pre-dose	Pre-dose	Pre-dose
C1D8	N/A	N/A	Approx. 4-6hr post dose	Approx 4-6hrs post dose	N/A	Pre-dose
C1D15	Approx. 4-6hr post dose	N/A	Approx. 4-6hr post dose	Approx 4-6hrs post dose	N/A	pre-dose
C2D1	N/A	Post dose e	Approx. 4-6hr post dose	Approx 4-6hrs post dose	Approx 4-6hrs post dose	Pre-dose
CXD1 c	N/A	Cy4 (+/- 1 Cy) e	Approx. 4-6hr post dose	Approx. 4-6hr post dose	Cycle 4 Day 1 only. Approx. 4-6hr post dose	N/A
End of treatment/disease progressiond	N/A	Post dose	Post dose	Post dose	Post dose	N/A

a Whole blood samples will be collected from sites of close proximity to Redx laboratory only

b Baseline tissue samples can be taken at any time after initial consent up to the first dosing. Investigator discretion should be used on likelihood of a patient being eligible

c CXD1 is Day 1 of each subsequent cycle

d Samples should be taken at the Final Study Visit, which should be performed as soon as practically possible after discontinuation of study drug (ideally within 7 days)

e Between 4-12 hours post dose

### 7.3.3.1.1 Exploratory endpoints from pharmacodynamic samples

Skin punch biopsies will be collected in Module 1. These samples may be analysed for gene and protein expression to determine target engagement of the Wnt pathway.

PBMC pharmacodynamic samples will be collected for all patients. These samples may be analysed for the effect of drug administration on induced PORCN/Wnt or related pathway activity.

Plasma samples may be used to analyse circulating soluble factors, such as relevant tumour markers and markers of immune function, in baseline and on-treatment samples. These may be analysed by enzyme linked immunosorbent assay (ELISA), or other relevant methods.

ctDNA samples may be used to analyse circulating tumour DNA/RNA (ctDNA/RNA). Total amounts and/or analysis of mutations/genetic alterations in ctDNA/RNA may be analysed and associated with response to treatment.

Fresh whole blood pharmacodynamic samples may be analysed by flow cytometry for changes in markers of immune cell populations, including, but not limited to, markers for immune cell subsets. In addition, assays of immune function such as stimulated cell activation (assessed by marker expression, cytokine secretion, proliferation, etc.) may be conducted using whole blood samples.

Paired tumour biopsies may be monitored for gene/protein changes. This data may be used to examine changes in Wnt pathway activation and/or immune cell changes in the tumour microenvironment.

Additional pharmacodynamic markers, (e.g., monitoring other inflammatory markers, measuring specific cell populations, RNA profiles of specific cell populations, or measuring cell surface markers that can be measured by flow cytometry, Western blot, or ELISA) may be evaluated at the discretion of the sponsor using excess pharmacodynamic or PK samples.

### **Tumour Samples**

An archival or a newly acquired biopsy will be requested from every patient enrolled in the study. These archived/newly acquired biopsies are optional (but encouraged) in the study.

Candidate biomarkers, e.g. upstream Wnt pathway aberrations (RNF43 mutation, RSPO fusion) will be analysed in archived/newly acquired tumour samples to investigate the relationship between these biomarkers and efficacy outcomes following treatment.

Paired tumour biopsy samples, where available, will be analysed for exploratory pharmacodynamic endpoint measurements as described in Section 7.3.3.1.1

### 7.3.3.2 Module 2

#### Blood and tumour Sample Collection

PBMC, circulating soluble factors, ctDNA and ctRNA samples for pharmacodynamic analysis will be collected from all patients at baseline and on treatment, according to the table of scheduled assessments.

Fresh whole blood will be collected from a subset of patients at baseline and on treatment, according to the table of scheduled assessments (depending on proximity of site for analysis of this fresh sample).

Optional paired tumour biopsies will be also collected, where possible, from any suitable patient enrolled into module 2.

As pharmacodynamic data become available, the timing of pharmacodynamic sampling may be adjusted, but the frequency of blood samples obtained will not increase.

